6.9.3 End-of-Treatment Visit

The EOT should be completed within \pm 7 days of the last dose of tarloxotinib. The following will be assessed or measured at EOT:

- Complete physical examination
- Weight
- Vital signs
- ECG (12-lead)
- Hematology panel
- Serum chemistry panel
- Pregnancy test
- Urine (dipstick acceptable)
- Blood sample for biomarkers (e.g., ctDNA)
- Concomitant medications
- Assess AEs
- Record the date and reason for the decision to discontinue study treatment

6.9.4 Safety Follow-up Visit

All patients will return to the investigational site 30 days (\pm 7 days) following the last tarloxotinib infusion for the Safety Follow-up Visit. At this visit, the following will be assessed or measured:

- Physical examination
- Weight
- Vital signs
- ECG (12-lead)
- Hematology panel
- Serum chemistry panel
- Urinalysis
- Assess AEs

Confidential and Proprietary

6.10 Concomitant Medications and Treatments

All medications (prescription and over-the-counter) and blood products taken within 14 days of Cycle 1 Day 1 until the EOT will be recorded. The reason(s) for treatment, dose, and dates of treatment will be recorded. In addition, concomitant medications used to treat AEs occurring up to 30 days after the last dose of tarloxotinib will be recorded.

6.10.1 Prohibited Medications

Concomitant medications and therapies excluded during the conduct of this trial include:

- Any other anticancer treatment including non-palliative radiation, chemotherapy, monoclonal antibodies, or TKIs
- Hormonal therapy for cancer

Note: Female patients who have been on hormone replacement therapy for menopausal symptoms for a period of at least 2 months will not be excluded from the study provided the planned hormone replacement therapy regimen remains largely unchanged during the conduct of the study

- Other tumor-targeted therapies
- Limited-field palliative radiotherapy to non-target lesions and bone-targeted agents, such as zoledronic acid and denosumab, are permitted.
 - Tarloxotinib should be delayed during radiotherapy and resumed upon completion of radiotherapy, if deemed appropriate by the treating physician after discussion with the Medical Monitor.
- Medications that prolong QT interval and have a risk of TdP (See Appendix B)

Patients should avoid all herbal remedies during study treatment; however, if herbal remedies are used, they should be documented as a concomitant medication. Patients and study staff should be instructed to notify all care providers that they are participating in a clinical study that has identified prohibited medications.

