- 8. Receiving medication that prolongs QT interval, with a risk of causing Torsade de Pointes (TdP), per protocol Appendix B, unless one of the following criteria are met:
 - a. Enrollment is allowed if discontinuation of such medication occurs at least 5 half-lives before Cycle 1 Day 1 OR
 - b. The patient is on a stable dose of a concomitant medication listed in Appendix B, prior to study entry and Sponsor approval is obtained Note: Exceptions may be made with Medical Monitor approval (e.g., for medications where the half-life is unknown or for QT prolonging medications not listed in Appendix B).
- 9. Personal or familial history of Long QT Syndrome, sudden death, or TdP
- 10. History of significant cardiovascular disease, including:
 - a. Cardiac failure New York Heart Association class III or IV or LVEF < 55%
 - b. Myocardial infarction, severe or unstable angina within 6 months prior to enrollment
 - c. TdP, ventricular arrhythmia (i.e., ventricular tachycardia or ventricular fibrillation)
 - d. Clinically significant thrombotic or embolic events within 3 months prior to enrollment

Amendment 3: 24 October 2020 Confidential and Proprietary

	Note: Significant thrombotic or embolic events include but are not limited to stroke or transient ischemic attack. Catheter-related thrombosis is not a cause for exclusion. Diagnosis of deep vein thrombosis or pulmonary embolism is allowed. e. Any uncontrolled or severe cardiovascular disease 11. Known concurrent malignancy that is expected to require active treatment within 2 years or may interfere with the interpretation of the efficacy and safety outcomes of this study in the opinion of the treating Investigator and confirmed by the Medical Monitor
	Note: Prior malignancy that is at a low risk of progression or recurrence (e.g., superficial bladder cancer, non-melanoma skin cancers, or low-grade prostate cancer not requiring therapy) may be allowed after discussion and approval by the Medical Monitor.

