2.5 Rationale for Dose Selection and QT Prolongation Mitigation

This study will evaluate tarloxotinib 150 mg/m² as a weekly 1-hour IV infusion (the MTD declared in the first-in-human Phase 1 study (Patterson 2013) and the dose level explored in the 2 Phase 2 studies). Preclinical xenograft studies utilizing weekly doses of tarloxotinib at human equivalent of the clinically assessed dose (48 mg/kg intraperitoneally weekly equivalent to 150 mg/m² IV weekly) induced marked tumor shrinkage and marked inhibition of EGFR phosphorylation for 7 days suggesting protracted tumor residence time for tarloxotinib-E. Furthermore, this dose was associated with low-grade skin rash and diarrhea, suggesting limited systemic EGFR inhibition, indicating an on-target pharmacodynamic effect in man. It is expected that enhanced activation in the tumor compared to normal tissue may offer a therapeutic advantage over standard TKIs in terms of the potential for enhanced intra-tumoral blockade of EGFR signaling with acceptable tolerability.

Tarloxotinib was associated with Grade 1 or Grade 2 QTc prolongation starting at a dose of 40 mg/m² and more consistent QTc prolongation at 150 mg/m² suggesting a dose-dependent effect. However, extending the infusion duration from 1 hour to 24 hours, which reduced the tarloxotinib C_{max} approximately 6-fold, did not appear to have an impact on QTc prolongation at the 200 mg/m² dose of tarloxotinib in the 2 patients evaluated. Time-matched assessment of QTc changes from baseline with tarloxotinib plasma concentrations after a 150 mg/m² dose from the Phase 2 studies did not suggest an exposure correlation. What is evident, is that there was a time-delay of the maximum QTc prolongation from baseline from the time to maximum tarloxotinib exposure of about 3 hours (QT prolongation hysteresis). During this period, patients are at greatest risk of developing QT-related cardiac arrhythmias, such as Torsade de Pointes (TdP). The QT prolongation risk mitigation strategy includes several layers of precautions, as follows:

- Eligibility criteria that exclude patients at increased risk, such as:
 - o History of long QT syndrome, TdP, or family history of sudden death
 - o Receiving medication that prolongs QTc interval
 - Baseline QTcF \geq 450 msec
 - o Significant cardiovascular disease
- Repeated ECG measurements during the study (prior to and following the infusion)
- Potassium supplementation prior to dosing, as needed (Section 6.4)

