 - **Note:** Patients who require steroid for CNS metastases must be on a stable or tapering dose of corticosteroids for at least 2 weeks prior to Cycle 1 Day 1 to be eligible for the trial. If applicable, patients must complete stereotactic radiosurgery 7 days prior to Cycle 1 Day 1 and whole brain radiotherapy 21 days prior to Cycle 1 Day 1.
- 8. Receiving medication that prolongs QT interval, with a risk of TdP per protocol Appendix B, unless one of the following criteria are met:
 - a. Enrollment is allowed if discontinuation of such medication occurs at least 5 half-lives before Cycle 1 Day 1 OR

Confidential and Proprietary

b. The patient is on a stable dose of a concomitant medication listed in Appendix B prior to study entry and Sponsor approval is obtained

Note: Exceptions may be made with Medical Monitor approval (e.g., for medications where the half-life is unknown or for QT prolonging medications not listed in Appendix B).

- 9. Personal or familial history of Long QT Syndrome, sudden death, or TdP
- 10. History of significant cardiovascular disease, including:
 - a. Cardiac failure New York Heart Association class III or IV or LVEF < 55%
 - b. Myocardial infarction, severe or unstable angina within 6 months prior to enrollment
 - c. TdP, ventricular arrhythmia (i.e., ventricular tachycardia or ventricular fibrillation)
 - d. Clinically significant thrombotic or embolic events within 3 months prior to enrollment

Note: Significant thrombotic or embolic events include but are not limited to stroke or transient ischemic attack. Catheter-related thrombosis is not a cause for exclusion. Diagnosis of deep vein thrombosis or pulmonary embolism is allowed.

- e. Any uncontrolled or severe cardiovascular disease
- 11. Known concurrent malignancy that is expected to require active treatment within 2 years or may interfere with the interpretation of the efficacy and safety outcomes of this study in the opinion of the treating Investigator and confirmed by the Medical Monitor

Note: Prior malignancy that is at a low risk of progression or recurrence (e.g., superficial bladder cancer, non-melanoma skin cancers, or low-grade prostate cancer not requiring therapy) may be allowed after discussion and approval of the Medical Monitor

- 12. Major surgery within 4 weeks prior to Cycle 1 Day 1
- 13. Infection requiring systemic treatment within 7 days prior to Cycle 1 Day 1

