9.2.2 Protocol Deviations

Deviations from the protocol including violations of inclusion/exclusion criteria will be assessed as "minor" or "major" in cooperation with the Sponsor. Deviations will be defined prior to database lock. Handling of major deviations in statistical analyses will be defined in the SAP.

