9.2.3 Analysis Sets

The primary efficacy analysis population includes all patients who received at least 1 dose of tarloxotinib. The Safety Population will consist of all patients who received at least 1 dose of tarloxotinib. The Safety Population will be the analysis population for the safety and primary efficacy analyses.

The Per Protocol (PP) Population is defined as patients who did not have a major protocol deviation that may affect interpretation of results. Efficacy will also be analyzed using the PP Population. A detailed specification of the PP Population will be provided prior to the database lock.

All enrolled patients who receive study treatment, have a baseline tumor assessment with documentation of measurable disease, have at least 1 on-study tumor assessment, whether or not this occurs at the specified imaging interval, and have no major protocol violations including inclusion/exclusion criteria or prohibited concomitant medication while on study, will be considered evaluable for response. Patients with a confirmed objective response (CR or PR) per RECIST criteria will be considered responders. Patients without a confirmed objective response, SD, or PD will be considered to be non-responders.

Patients who are treated and removed from the study prior to on-study tumor assessments because of clinical disease progression will be considered non-responders. Patients who are treated and removed from study prior to on-study tumor assessments for reasons other than clinical progression will be considered unevaluable for response and may be replaced. In addition, if a patient is enrolled without central laboratory confirmation of the specific gene alteration, and then is subsequently found not to have the specific gene alteration by central review, this patient will be considered unevaluable for response and may be replaced.

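### Exclusion 8b admits patients on a stable torsade-risk drug that Section 6.10.1 prohibits during the trial, and nothing in the protocol reconciles the two rules

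*Protocol*

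**What the plan says.** Protocol 5.2, exclusion 8, states a general bar with exceptions: "Receiving medication that prolongs QT interval, with a risk of TdP per protocol Appendix B, unless one of the following criteria are met". Two exceptions follow, joined by OR. Under 8a the drug is withdrawn five or more half-lives ahead of the first dose. Under 8b, "The patient is on a stable dose of a concomitant medication listed in Appendix B prior to study entry and Sponsor approval is obtained". The synopsis carries the same two routes.

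Protocol 6.10.1 opens its list with "Concomitant medications and therapies excluded during the conduct of this trial include", and one entry is "Medications that prolong QT interval and have a risk of TdP (See Appendix B". That entry has no condition about a stable dose, Sponsor approval or newly started drugs.

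Protocol 2.5 describes layers of QT risk mitigation. The first layer is eligibility criteria that keep out patients at higher risk, and one example given is "Receiving medication that prolongs QTc interval". The 8b exception is not mentioned there.

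Protocol 9.2.3 makes evaluability for response conditional. Patients must, among other things, "have no major protocol violations including inclusion/exclusion criteria or prohibited concomitant medication while on study".

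**The concern.** A site with a patient admitted under 8b cannot satisfy both rules while the patient stays on the drug. One section says the patient may enter on it, and another says the drug may not be taken during the trial.

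The subject matter makes this more than untidy drafting. Section 2.5 calls QT prolongation the main identified risk, and Section 2.3.2 reports that T-wave analysis points to hERG blockade. Section 5.3 also makes a significant deviation a ground for stopping study treatment unless the Investigator and the Medical Monitor agree and the IRB or IEC approves. A site cannot tell whether Sponsor approval under 8b already settles that.

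There is a secondary analysis question. Section 9.2.3 ties evaluability to freedom from major violations and names prohibited medication. A patient whom the Sponsor knowingly admitted could therefore, on one reading, be called unevaluable because of the approved drug.

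**Working it through.** The point is textual, so the passages are set side by side first.

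1. **Whom 8b covers.** Route 8a already deals with patients who stop the drug. Since 8b is an alternative to it, 8b has a separate meaning only for patients who have not gone through that washout. It does not ask them to stop.

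2. **What 6.10.1 covers.** It refers to the same appendix, so the drugs are identical. Other parts of its list state permissions: established hormone replacement, limited palliative radiotherapy and bone-targeted agents. An 8b permission could have been written there and was not.

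3. **The two together.** Take a patient on a stable Appendix B drug, approved by the Sponsor, who continues it. Under 5.2 the patient is eligible. Under 6.10.1 the drug is prohibited. Section 6.8 treats every departure from the protocol as a deviation, and Section 11.2 requires exact adherence. The patient is therefore eligible and deviating from the first dose.

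4. **Section 2.5.** Its item omits the exception, so the summary is stricter than the criterion it summarises.

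5. **Analysis consequence under the protocol.** For the patient to leave the ORR denominator, all of the following must hold:
   - the deviation is graded major (9.2.2 has this decided together with the Sponsor, with deviations defined before database lock);
   - the 9.2.3 evaluability rule is applied;
   - the 9.6.1.2 denominator of evaluable patients is used, although 9.2.3 itself names the Safety Population (anyone given a dose) for the primary efficacy analysis.

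6. **Analysis consequence under the SAP.** SAP 9.2.10.1 gives the evaluability definition without any medication or deviation condition. SAP 9.2.11.1 divides by enrolled subjects. Its cross-reference points to 9.2.10, the evaluable-subject definition, but that section has no medication condition either. SAP 15 puts all treated subjects in the ORR analysis and drops the Per Protocol analysis. SAP 4 says the SAP governs where the two documents differ. On every one of these statements the 8b patient stays in.

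For scale, the protocol's design figures (Section 9.1) were reproduced. The inputs are n1 = 21, stop at 3 or fewer responses, n = 43, reject at 11 or more. With X1 ~ Bin(21, p) and X2 ~ Bin(22, p):

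P(reject) = Σ (x = 4 to 21) P(X1 = x) × P(X2 ≥ max(0, 11 − x))

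| Quantity | Computed | Stated |
|---|---|---|
| P(reject) at p = 0.15 | 0.0454 | 0.0454 |
| P(reject) at p = 0.31 | 0.8014 | 0.8014 |
| P(X1 ≤ 3) at p = 0.15 | 0.611 | 0.61 |

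The documents do not say how many patients entered under 8b. As an assumption only, suppose k patients per cohort were removed in the second stage (22 − k in place of 22), were not replaced, and the cut-off stayed at 11. Power at 31% would be:

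| k | 0 | 1 | 2 | 3 | 4 |
|---|---|---|---|---|---|
| Power | 0.801 | 0.779 | 0.754 | 0.725 | 0.694 |

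If such patients were replaced, the design figures would not change. Section 4.1 permits replacement in general terms for patients not evaluable for tumour response. It plans about 248 enrolled for 215 evaluable, an allowance of 33/248 = 13.3%. Under the SAP no efficacy test is performed, so none of these losses arises.

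**The case against.** The strongest reply is that 8b is a specific permission that should be read into the general prohibition, and that the gap is only a missing cross-reference. That is a sensible guess at intent, but the protocol gives no rule of precedence, and 6.10.1 writes out its other permissions. The reply shows that repair is easy. It does not show that the text is consistent.

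Several limits on the point do stand:

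- **Removal from the primary analysis.** A reader might infer that Sponsor approval at entry ends in removal from the primary analysis, perhaps after response is known. The documents do not support this. Only violations graded major count, nothing says an approved drug would be graded major, 9.2.3 also names the Safety Population, and the SAP removes the condition.
- **Replacement under 9.2.3.** A reader might infer that 9.2.3 itself lets the patient be replaced. Its replacement sentences cover removal before an on-study tumour assessment for reasons other than clinical progression, and failed central confirmation of the gene alteration. Only the general sentence in 4.1 could reach prohibited medication.
- **Section 2.5 as a third conflicting rule.** The item is one example in an abridged list of eligibility criteria. It should be aligned, but it is not an independent rule.
- **Unmonitored patients.** The entry and pre-infusion QTcF limits, electrolyte checks, serial ECGs and the case-by-case approval in 8b remain in place.
- **Timing.** The study stopped with 41 subjects enrolled and the database is locked (SAP 4), so a correction changes no planned efficacy output.

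**Conclusion.** The inconsistency holds on the current text and does not depend on the amendment history. Exclusion 8b and Section 6.10.1 cannot both be followed for a patient who stays on an approved Appendix B drug, and Section 2.5 omits the exception.

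Its size in patients is unknown. A reader might take the QT rates in the two earlier Phase 2 studies as a measure: prolongation in 35 of 51 patients (68.6%), and QTcF of at least 501 msec in 21%. They are not one. They describe QT findings on the study drug, and the protocol does not give those studies' co-medication rules.

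The effect on the reported ORR is nil under the governing SAP. Under the protocol alone it is possible but conditional on the three steps in item 5 of the working, and the power table applies only if those steps occur without replacement.

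One reporting consequence remains. SAP 11.2 neither lists nor summarises deviations, and the QTcF summaries in SAP 14.4 do not specify separating patients on Appendix B drugs. The medication listing in SAP 12.2 would show the drugs themselves, but not whether their use was treated as permitted or prohibited.

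**What to change.** Reconcile exclusion 8b in Section 5.2, and its copy in the synopsis, with Section 6.10.1 so that one rule covers both entry and use during the trial. Align the Section 2.5 summary with that rule. State in Section 9.2.3 whether a Sponsor-approved Appendix B drug counts as a prohibited medication when evaluability is judged. Which clinical rule applies is for the medical team to decide; this review takes no position on it.

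The cost is wording in the synopsis and four protocol sections. No sample-size figure or SAP analysis changes. With the database locked, the benefit is a clear record of how such patients were handled and sound text if the protocol is reused.

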7. ASSESSMENT OF EFFICACY

Tumor assessment and imaging will be performed according to institutional practice and will include CT or MRI of the chest and abdomen, brain scan, and bone scan at baseline. The baseline radiographic tumor assessment is required within 28 days prior to the first dose of tarloxotinib. Brain and bone scans do not need to be repeated for patients with no brain or bone metastases at baseline. Recently completed negative positron emissions tomography (PET) scans can be substituted for baseline bone scans. Subsequent radiographic tumor assessments will be every 8 weeks (±5 days) with respect to Cycle 1 Day 1, until unequivocal PD is documented. The same imaging modality used for baseline imaging (i.e., CT or MRI) must be used for subsequent tumor assessments in each patient. In accordance with RECIST v1.1, response (PR and CR) must be confirmed by a second tumor assessment at least 8 weeks after the initial observed response. The scheduling of subsequent tumor assessments may be adjusted based on the date of the most recent imaging. Investigators are instructed to ensure that original

Confidential and Proprietary

images (or high-quality copies) of all baseline and on-study scans are filed and available for transmission to the Sponsor (or designee) for a future possible central reading.

Efficacy assessment will be according to the local Investigator.

7.1 Primary Efficacy: Objective Response

The primary efficacy variable, ORR, is defined as a CR or PR according to RECIST v1.1 recorded from baseline until disease progression or death due to any cause.

7.2 Secondary Efficacy

Secondary efficacy variables include:

- BOR as measured by CR, PR, and SD
- DOR as measured from the date of first response to date of disease progression or death
- DCR based on patients who had CR or PR or SD for at least 2 cycles (8 weeks)
- PFS as measured from the date of first study drug dose to the date of the first objective documentation of radiographic disease progression or death due to any cause
- OS as measured from the date of first study drug dose to the date of death by any cause

8. ASSESSMENT OF SAFETY AND EXPLORATORY VARIABLES

8.1 Adverse Events

Investigators will collect information related to AEs will be collected throughout this clinical trial. The terms and definitions are consistent with the US DHHS guidance (2012).

All AEs occurring in all patients will be collected following exposure to study treatment (treatment emergent) until approximately 30 days after the last study treatment. Changes in the patient's medical condition that occur prior to the first exposure to study treatment will be reported as medical history. At each post-treatment visits, patients will be asked about any possible AEs in a non-leading manner. An example of a non-leading method of eliciting AE information is "Have there been any changes in your health since you were here last?" Patients should also be asked about the severity and/or persistence of any AEs that were ongoing at the time of their last visit.

All AEs will be followed until stabilization or resolution.

